8.3.3 Primary and clinical secondary endpoint assessment

At enrolment, participating subjects will be instructed on how and when to fill in and mail the questionnaires to the CRO.

A questionnaire will be completed by the patient him-/herself at home separately after each single experienced syncope or pre-syncope event. Every 3 months starting from enrolment date patients will mail the collected questionnaires to the CRO using the pre-paid and pre-addressed envelopes provided at enrolment. If a patient will not experience any syncopal or pre-syncopal event during a 3-month period, he/she will complete a single questionnaire documenting the absence of any recurrence.

Patients will be instructed to mail only anonymous questionnaires and envelopes.

CRO personnel will monitor the timing of questionnaire flow. In case of delays, the CRO staff will inform the investigator, who will contact the patient to solicit the questionnaire or to fix any related problems. The CRO will also inform the investigators about the occurrence of a syncope or pre-syncope event.

Responses to the questionnaire will determine whether or not the event description and the associated symptoms are consistent with a primary or secondary endpoint event.

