9.6 Primary endpoint collection

Self-administered anonymous patient questionnaires will be collected every 3 months after post-implant hospital discharge (within a ± 14 day interval) by independent personnel of a CRO as described in section 8.3.3.

Syncope and pre-syncope assessment will be exclusively based on what patients will refer by self-administering the questionnaire, at home, separately for each event.

Despite patients will be instructed to fill in the study questionnaire, they might react differently to a syncope recurrence during the study. The following Table 4 reports the most awaited situations and illustrates the subsequent steps accordingly.

Table 4. After a syncopal and pre-syncopal recurrence

| Situation: | The patient fills in the questionnaire | The patient shows up for a medical examination |
|------------|---|---|
| 1 step | The CRO quarterly collects patient questionnaires | The investigator recommends the patient to mail the questionnaire to the CRO in due time and reports any AE |
| 2 step | If an AE occurred, the CRO informs the investigator | |

Any change of the programmed pacing mode not justified by a primary endpoint (even when a-posteriori assessed), will be considered as a crossover, but analyzed according to the Intention-To-Treat (ITT) principle, see Section 11)

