9.9 Primary and clinical secondary endpoint Adjudication Board

All the unclassified syncope or pre-syncope episodes (see section 8.3.3) will be adjudicated by an Adjudication Board of at least 3 members. The members will be selected among experienced physicians with documented expertise in syncope. The members will not participate in the study as Investigators

The Adjudication Board will review unclassified endpoint events according to a charter provided in a separate document.

The members will remain blinded to the randomization, even if they will have access to the electronic CRF.

The adjudication process will be requested by the study Project Manager after the required number of primary endpoint events for the interim analyses has exceeded the predefined levels (see section 11.6).

The interim analyses will be performed only with the events collected at the times of the call for the adjudication from the Project Manager. Further events possibly occurring thereafter will not be included.

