11 STATISTICAL CONSIDERATIONS

11.1 Statistical design, method and analytical procedures

Standard summary statistics will be calculated for all patients and study outcome variables. Categorical data will be summarized via distributions of absolute and relative frequencies. For all relevant parameters 95% confidence intervals will be calculated.

For the analysis of the primary endpoint and the secondary endpoint the Kaplan-Meier plots will be generated and the estimated survival functions of the study groups tested with the two-sided log-rank test. Dependence of survival on major baseline predictors will be studied with proportional hazard Cox models. Hazard ratios and relative 95% confidence intervals for each predictor will be calculated, respectively. Data will be censored at the date of last patient contact. The ITT principle will be applied.

Statistical calculations will be carried out by using STATA 11.1 ®, SAS 9.3 © or R.

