11.7.1 Stopping Rules

1. The CCI will be informed monthly by the CRO about the total number of patients who will experience a syncope recurrence (primary endpoint event).
2. When the number of events will reach¹ the predefined limits for interim analyses (40% and 70% of the expected number of events), open queries will be resolved and on site monitoring visits for source data verification will be performed.
3. Unclassified primary endpoint events will be adjudicated (see section 9.9). If available primary endpoint events will be less than the predefined limits for interim analyses after the adjudication process, endpoint point event collection will continue until the required number will be reached.
4. When data set will be cleaned the clinical project manager of the study will inform the appointed independent statistician.
5. The independent statistician will analyze the data according to the Statistical Analysis Plan (SAP). The results will be communicated to the CCI and the sponsor of the study. If the

¹ The number of events may exceed the programmed limit whenever 2 or more events occur at the same time.

primary objective is reached the study stops immediately. The stop date of the study is the date of insertion in the database of the last syncopal recurrence. If the primary objective is not reached the independent statistician will recommend to continue the study until 62 events will be collected. Investigators will not be informed of the results of the interim analyses.

6. After study closure investigators shall complete missing data (apart from the primary events) and close open queries within the following 2 months. Events occurring after the stop date shall not be considered either for primary or for secondary endpoints.

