7.5 Evaluation of study objectives

The BIOSync CLS study (BA103, CIP ver. 7.0) gathers primary and secondary endpoints' data through self-administered patient questionnaires. In order to ensure double-blinding in endpoint assessment, the questionnaires will be collected by external personnel of an appointed CRO. This process is descripted in detail in the Charter for patient questionnaire collection and adjudication, version 2.0, 06-Mar-2017, and summarized in the below image.

At the end of the adjudication the following derived variables will be created.

Variable name	List of values	Unit of measure	Description	
pe	0 (No); 1 (Yes)	*	Occurrence of syncope episode	
time_pe	Numeric	days	If pe=1: time to the first post	
			randomization recurrence of a	
			syncopal episode;	
			If pe=0: total follow-up time	
se	0 (No); 1 (Yes)	-	Occurrence of pre-syncope or	
			syncope episode	
time_pe	Numeric	days	If pe=1: time to the first post	
			randomization recurrence of a pre-	
			syncope or syncope episode	
			whichever comes first.;	
			If pe=0: total follow-up time	

The analysis of the primary and secondary study objectives will be performed with the following code (STATA language).

stset time_pe, failure(pe==1)

*Kaplan_meier plots generation

sts graph by(rd_display), ci risktable

*Comparison of survivors functions

sts test rd_display, logrank

*Proportional hazard Cox models for major baseline predictors

stcox rd display

estat phtest

stcox gi_age

stcox gi_gender

stcox hs syncop life

stcox hs_syncop_lastyear

stcox ecg_mean_hr

stcox tt_response

stcox tt_pause_max

stcox tt_pause_type

stcox tt_time_pre_sync

^{*}Study objectives evaluation

^{*}Primary endpoint

*Secondary endpoint

stset time_se, failure(se==1)

*Kaplan_meier plots generation
sts graph, by(rd_display) ci

*Comparison of survivors functions
sts test rd_display, logrank

*Proportional hazard Cox models for major baseline predictors
stcox rd_display
estat phtest
stcox gi_age
stcox gi_gender

stcox hs_syncop_lastyear stcox ecg_mean_hr

stcox tt_response stcox tt_pause_max

stcox hs_syncop_life

stcox tt_pause_type stcox tt_time_pre_sync

stcox tt_low_bp

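### Syncopes arrive by quarterly questionnaire, but neither the data cut-off nor the censoring date is tied to questionnaire coverage, so an early stop may omit real events and add unobserved event-free time

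*Protocol*

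**What the plan says.** **How syncope is known.** Protocol 9.6 rests the assessment solely on questionnaires that patients complete at home. Protocol 8.3.3: "Every 3 months starting from enrolment date patients will mail the collected questionnaires to the CRO". Protocol 9.6 says the questionnaires "will be collected every 3 months after post-implant hospital discharge (within a ± 14 day interval". The two sections start the quarters from different dates, enrolment and discharge.

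**How the data are cut.** Protocol 9.9: "The interim analyses will be performed only with the events collected at the times of the call for the adjudication from the Project Manager". Protocol 11.7.1, item 5: "The stop date of the study is the date of insertion in the database of the last syncopal recurrence". Item 6 adds "After study closure investigators shall complete missing data (apart from the primary events) and close open queries within the following 2 months", and then "Events occurring after the stop date shall not be considered either for primary or for secondary endpoints".

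**How event-free time ends.** Protocol 11.1: "Data will be censored at the date of last patient contact". SAP 7.1 repeats this. For patients without a syncope, SAP 7.5 derives the primary time variable as "If pe=0: total follow-up time". Neither document defines a contact, says when total follow-up ends, or links either to the last questionnaire or to the stop date.

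**The concern.** The plan runs on three clocks. Interim data are cut by collection, the stop date is set by database entry, and the exclusion in item 6 works by occurrence. Consider a syncope that happens before the stop date and is reported after it. Item 6 does not exclude it, Protocol 9.9 keeps it out of an interim dataset, and no procedure brings it in at closure.

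The time at risk has a matching gap. Only a returned questionnaire shows that a patient was free of syncope, but a contact can fall after the last one. Under Protocol 8.3.3 the investigator contacts the patient when a questionnaire is late, and a hospital visit can also come later than the last mailing. Time counted up to such a contact is time in which a syncope could have occurred but could not yet have been recorded.

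Two statisticians could therefore build different primary datasets from the same plan, and item 5 sends interim results to the coordinating investigator and the sponsor. Absolute 2-year survival, the quantity in the hypotheses (Protocol 7.2.1, SAP 3.2), is most exposed, and most of all if the trial stops early.

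**Working it through.** **Inputs from the documents.** 2-year incidence 57% control and 34% CLS; exponential times; 2-year accrual; 1:1 allocation; 10% loss; 128 patients (Protocol 11.2). Follow-up ends at 24 months or the first primary event (8.8.6). Looks at 25, 43 and 62 events (11.6). Quarterly mailing (8.3.3, 9.6).

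**Assumption.** The documents give no time from mailing to database entry. Three settings were tried: 0 days, 0–28 days and 14–60 days.

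**The plan's own figure.** Hazards: −ln(0.43)/2 = 0.422 and −ln(0.66)/2 = 0.208 per year; ratio 0.492. Events = (1.960 + 0.842)² / (0.25 × ln(0.49)²) = 61.7, so 62. (This squares the logarithm; the printed formula omits the square.) The 62 reproduces.

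**Simulation.** 4,000 trials of 128 patients per setting. Loss is exponential, 10% by 2 years. Each syncope is reported at the end of its quarter, counted from entry, plus the lag. The trial stops at the 25th, 43rd or 62nd reported event. Three datasets were compared at the stop date:

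- A: every syncope that has occurred.
- B: entered syncopes only, all other patients event-free to the stop date (or to their own loss or 24-month end).
- C: entered syncopes only, all other patients censored at the last questionnaire due.

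Mean number of syncopes that have occurred but are not entered:

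| Lag | 25 events | 43 events | 62 events |
|---|---|---|---|
| 0 days | 3.2 | 2.2 | 0.7 |
| 0–28 days | 4.3 | 2.8 | 0.9 |
| 14–60 days | 5.9 | 3.8 | 1.2 |

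For 0–28 days the 5th–95th percentiles are 1–8, 0–6 and 0–3. The 62-event column is conditional: only about 14% of simulated trials reached 62.

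Events per person-year, 0–28 day lag:

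| Stop at | Control A / B / C | CLS A / B / C | B below A |
|---|---|---|---|
| 25 | 0.437 / 0.374 / 0.445 | 0.215 / 0.182 / 0.218 | 14–15% |
| 43 | 0.434 / 0.407 / 0.438 | 0.214 / 0.199 / 0.216 | 6–7% |
| 62 | 0.511 / 0.504 / 0.516 | 0.264 / 0.260 / 0.267 | 1–2% |

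Across the three lags, B falls short by about 12–20% at 25 events, 5–9% at 43 and 1–2% at 62. Under C, rates are within about 1–2% of A.

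**Hand check.** The missing share of events should roughly equal the shortfall in the rate: 4.3/29.3 = 14.7%, 2.8/45.8 = 6.1%, 0.9/62.9 = 1.4%. These agree with the table.

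**Effect on the comparison (0–28 day lag).**

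- Hazard ratio, A against B: 0.486 and 0.480 at 25 events; 0.487 and 0.484 at 43; 0.511 and 0.510 at 62.
- Mean log-rank Z, A against B: −1.85 and −1.71 at 25 events; −2.35 and −2.28 at 43.
- Chance of crossing, A against B: 5.6% and 5.1% at 25 events; 46% and 43% at 43. Under C these are 4.9% and 43%, because C does not recover the missing events.
- With no treatment effect, each look taken alone: 0.1%, 1.4% and 4.6% under A; 0.1%, 1.2% and 4.4% under B. Unentered syncopes are then 5.1, 5.0 and 2.3, equally split between arms.

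**The case against.** A reader might infer that item 6 forbids adding any syncope after closure and that the affected patients are counted event-free to the stop date. The documents support neither. Item 6 is addressed to investigators, who do not assess primary events (Protocol 8.3.2). Its exclusion covers only events occurring after the stop date. Late receipt by the CRO is not addressed, which differs from being barred. No passage runs event-free time to the stop date; if last contact means the last returned questionnaire, almost no bias in the rates arises.

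A reader might also infer a biased treatment effect or a raised false-positive rate. The simulation shows neither when reporting delay is equal by arm. Freezing interim data when adjudication is called is pre-specified, and if the trial continues, late reports can enter at the next look. A stop at 25 events is unlikely (about 5% under the planned effect), and the distortion at 62 is small.

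All of this stands and limits the point. What remains is that Protocol 9.9 does cut interim data by collection, and that contact, total follow-up and the treatment of late reports are undefined. Equal delay by arm is also an assumption: investigators know the allocation and are the ones who chase late questionnaires.

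**Conclusion.** The point holds as a gap in the cut-off and censoring rules. At a stop on 25 or 43 events, about 4 or 3 real syncopes may be left out. If follow-up is run to the stop date, event rates come out about 14–15% or 6–7% too low, similarly in both arms. At 62 events the figures are about 1 syncope and at most 2%.

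The consequence is overstated absolute survival and a small loss of power at the interim looks. It is not a distorted hazard ratio or an inflated type I error. The sizes rest on the planned event rates, an assumed 0–28 day lag and equal delay by arm. The rate bias also depends on the reading of follow-up and nearly disappears if patients are censored at the last questionnaire. The repair is cheap and worth making before any look.

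**What to change.** Amend Protocol 9.9, 11.1 and 11.7.1 and SAP 7.1 and 7.5, with the boundary wording in Protocol 11.6 and SAP 7.6:

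1. Define the analysis cut-off by date of syncope occurrence, and fix that date when the target count is reached.
2. Before data are unblinded for analysis, have the blinded CRO collect the questionnaires covering the period up to that date, with unclassified episodes adjudicated. Include every syncope on or before it.
3. Censor event-free patients at the end of the last period covered by a returned questionnaire, not at last contact. State whether quarters run from enrolment or from discharge.
4. Compute the Lan-DeMets boundary at the actual count. With the average late reports added, the information fractions would be about 29.3/62 = 0.47 and 45.8/62 = 0.74 instead of 0.40 and 0.70.

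Keep the exception for primary events in item 6. Deleting it would ask unblinded investigators to complete primary events after results may have been communicated.

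The cost is wording, plus a wait of up to about three months at each look, partly overlapping the query resolution and monitoring in item 2. The two months in item 6 come after closure and do not absorb it. Protocol 6.3 lists early termination for efficacy among its risk controls, so the delay has to be weighed. If it is not acceptable, step 3 alone removes most of the bias in the rates without delay, but it does not recover the missing events or the small power loss.

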11.8 Procedures for reporting of deviations to the statistical plan

Deviations from the statistical plan are documented accordingly.

11.9 Specification of subgroups

No subgroups are pre-specified.

11.10 Procedure for accounting of all data for analysis

The required strict adherence to the monitoring plans of the respective reference studies will ensure acquisition of all data.

11.11 Handling of missing, unused and spurious data

Missing or spurious data is not substituted; all data – as far as correctly measured – is analyzed.

11.12 Exclusion of data from confirmatory data analysis

In some cases, particular clinical data is excluded from analysis. The following reasons are possible:

- Data is not measured as described in this clinical investigation plan.
- Data is evaluated beyond the required follow-up schedule.
- Patient has to be excluded because she/he does not fulfill the exclusion/inclusion criteria.
- Patient requires that all recorded data has to be deleted.
- There is no valid patient consent form available.

11.13 Minimum and maximum number of patients per site

It may be expected that every 100 over-40 subjects undergoing a head up tilt test and reporting 3 or more syncopal episodes, about 50 of them would be positive, 12 would be eligible with a type 2B cardio-inhibitory response⁽¹⁸⁾, 6 would accept to implant a pacemaker and about 3 to participate to the study, undergoing the randomization⁽¹⁹⁾. Therefore only centers performing a high number of tilt test examinations per year (≥ 200 per year) may participate in the trial to effectively contribute to enrolment in a reasonable time period. Each

center should enroll at least 5 patients in the course of the study, in a competitive enrolment process.

12 DATA MANAGEMENT

The established Clinical Data Management System (CDMS) is "iMedNet" of the vendor MedNet Solutions, Inc. As a pure internet-based application that is used with the current versions of most internet browsers, there is no specific local software to support (cloud based "Software as a Service" SaaS). iMedNet supports industry standards (FDA 21CFR11, HIPAA and Safe Harbor).

12.1 Procedures used for data review, database cleaning, and issuing and resolving data queries

After data entry into the CDMS, the clinical data is automatically checked with programmed quality checks. Errors, discrepancies, missing data, and entries out of range are resolved by automatically (CDMS) and manually (clinical monitor, data manager) generating data queries.

The system supports detailed tracking of the query process. Corrections to eCRF can only be done by the designated site personnel and need to be signed by the investigator. All changes are automatically recorded in the system's audit-trail.

12.2 Procedures for verification, validation and securing of electronic data systems

The Clinical Data Management System (CDMS) is hosted on a dedicated database server at the vendor MedNet Solutions, Inc. Only authorized users with fixed roles have access to the clinical database. The access is controlled and maintained by the Clinical Data Management. Every access is automatically logged and changes of the clinical data are stored in independent audit trails. The CDMS is verified and validated accordingly. The user interface and the internal business logic of the clinical database is validated accordingly and verified during the study related development and before release for data entry.

An authenticated user account is created and maintained by BIOTRONIK for each authorized user once the user has completed appropriate training. Users are obligated to keep their password confidential.

Depending on their role within the investigational study, users are limited to "read only" or may be given permits to enter or update data, provide resolutions to queries and apply electronic signatures. Only investigators are allowed to sign the entries.

12.3 Procedures for data retention

All study related electronic documents are stored in the archive of BIOTRONIK which provides storage conditions free from risk of fire, flood, theft and vermin. The access to the files is controlled.

After database closure, all eCRF data and the audit trail and other relevant database content are exported and stored electronically on the archive server.

12.4 Specified retention period

All electronic documents and exported data from relevant databases are stored for at least 15 years. At the end of this period, requirements from laws and other regulations will be reconsidered in order to decide whether the retention period must be extended or data must be deleted.

13 AMENDMENT PROCEDURES

If throughout the course of the study changes to the Clinical Investigation Plan (CIP) are deemed to be necessary, a change justification has to be prepared which includes the rationale and content of the adjustment. The modification of the CIP can either be summarized in a separate document as an attachment to the current applicable version of the CIP or result in a new version of the CIP.

If the changes have impact on study related procedures or data analysis they are substantial by definition.

New versions of the CIP or substantial amendments have to be reviewed and confirmed by the Coordinating Clinical Investigator. All investigators have to acknowledge the receipt of an amendment by signing an amendment agreement form.

Before implementation of any changes, substantial amendments have to be approved by the Ethics Committee (EC) and – if applicable – by the Competent Authority (CA). Non substantial amendments are submitted for notification only.

The investigator should not implement any deviation from or changes to the CIP without agreement of the sponsor and prior review and documented approval from the EC (and CA if required). The only exception is the necessity to eliminate an immediate hazard to the subjects, or when the change involves only logistical or administrative aspects of the study.

14 DEVIATIONS FROM CLINICAL INVESTIGATION PLAN

14.1 13.1 CIP compliance and exceptions

All sponsor personnel, all investigational site personnel as well as other third parties, who are involved in tasks covered by this CIP, are generally obliged to comply with this CIP.

A **deviation** is any failure to follow, intentionally or unintentionally, the requirements of the CIP, including laws, guidelines and other regulation as far as required by the CIP, as well as applicable amendments. Deviations that are likely to seriously affect or that actually have seriously affected the rights or safety or wellbeing of subjects or the scientific integrity of the clinical investigation are **major** deviations. Otherwise they are **minor** deviations.

Erroneous, spurious or missing data in a CRF is not a deviation in itself and is handled according to the query processes described in the data management section of this CIP. However, the underlying reason might be a deviation.

Under **emergency** circumstances, deviations from the CIP to protect the rights, safety and well-being of human subjects may proceed without prior approval of the sponsor and the ethics committee.

